## 3.0 Inclusion and Exclusion Criteria

Create a numbered list below in sections 3.1 and 3.2 of criteria subjects must meet to be eligible for study enrollment (e.g., age, gender, diagnosis, etc.).

### Vulnerable Populations:

Indicate specifically whether you will include any of the following vulnerable populations in this research. You MAY NOT include members of these populations as subjects in your research unless you indicate this in your inclusion criteria because specific regulations apply to studies that involve vulnerable populations.

The checklists referenced below outline the determinations to be made by the IRB when reviewing research involving these populations. Review the checklists as these will help to inform your responses throughout the remainder of the protocol.

- **Children** –Review “HRP-416- Checklist - Children”
- **Pregnant Women** – Review “HRP-412- Checklist - Pregnant Women”
- **Cognitively Impaired Adults**- Review “HRP-417- Checklist - Cognitively Impaired Adults”
- **Prisoners**- Review “HRP-415- Checklist - Prisoners”
- **Neonates of uncertain viability or non-viable neonates**- Review “HRP-413- Checklist - Non-Viable Neonates” or “HRP-414- Checklist - Neonates of Uncertain Viability”

### 3.1 Inclusion Criteria

Create a numbered list of the inclusion criteria that define who will be included in your final study sample (e.g., age, gender, condition, etc.)

1. Adult ( $\geq 18$  years of age) patients with diagnosed HCC, who are treated with their first round of TACE.
2. Sex: male or female
3. BMI  $\leq 40$

### 3.2 Exclusion Criteria

Create a numbered list of the exclusion criteria that define who will be excluded in your study.

1. Children ( $<18$ )
2. Patients who do not speak English
3. Patients with a history of hypersensitivity reactions to sulfur hexafluoride lipid microsphere components or to any of the inactive ingredients in Lumason.
4. Patients with unstable cardiopulmonary conditions (acute myocardial infarction, acute coronary artery syndromes, worsening or unstable congestive heart failure, or serious ventricular arrhythmias)
5. Patients who have a prior non-contrast ultrasound, within last 3 months (at time of consent), where the tumor could not be seen – most commonly due to severe steatosis or obesity.
6. Pregnant or nursing woman
7. Patients who do not plan to get their follow-up CT/MRI at Hershey Medical Center.

### 3.3 Early Withdrawal of Subjects

#### 3.3.1 Criteria for removal from study

Insert subject withdrawal criteria (e.g., safety reasons, failure of subject to adhere to protocol requirements, subject consent withdrawal, disease progression, etc.).

Patients who are successfully enrolled in the study at the time of TACE will be excluded if the treated lesion is not visible on the grayscale ultrasound at timepoint 1, and contrast would therefore not be administered.

Additionally, if patients do not return for their scheduled CT/MRI, following TACE treatment, they will be removed from the study.

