## 1.0 Objectives

### 1.1 Study Objectives

Describe the purpose, specific aims or objectives. State the hypotheses to be tested.

In this study, we propose a prospective trial to determine if contrast enhanced ultrasound (CEUS) is non-inferior to CT or MRI in patients with hepatocellular carcinoma (HCC) following transcatheter arterial chemoembolization (TACE) treatments, in a U.S. population, using Lumason contrast agent. This would be the largest trial to date examining this patient population in the U.S.

The primary objective of our study is to estimate the sensitivity and specificity of the CEUS (Research Timepoint 1) and evaluate for non-inferiority between CEUS and the clinical gold standard of CT/MRI using the Liver Reporting & Data System (LIRAD). We will be assessing the presence of treated or residual tumor, new sites of disease, and portal vein thrombus. Patient factors, such as BMI, underlying liver disease type, alpha fetoprotein level, and size of liver will be recorded. If findings of metastatic disease external to the liver are identified on CT or MRI and not seen on CEUS, they will be recorded.

CEUS, like regular ultrasound, only images specific organs and cannot identify necessarily metastatic disease, as ultrasound cannot image bones and lungs for this purpose.

The second objective of the project will compare the CEUS with a second, standard of care, follow-up CT or MRI (performed 2-4 months later [Research Timepoint 2]). CT can have false negatives due to ethiodol obscuring subtle, early disease and it is possible that CEUS could identify residual disease earlier compared to the gold standards, but would be characterized as a false positive if compared only to the initial imaging (Timepoint 1). This follow-up will evaluate for false positives or negatives on any of the modalities.

The third objective of the project will evaluate patient subjective data in regards to imaging modality preference and possible effects on compliance. The survey will be administered at the conclusion of Timepoint 1 and will include questions about anxiety, comfort, compliance, and modality preference, graded on a Likert scale.

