#### 3.3.2 Follow-up for withdrawn subjects

Describe when and how to withdraw subjects from the study; the type and timing of the data to be collected for withdrawal of subjects; whether and how subjects are to be replaced; the follow-up for subjects withdrawn from investigational treatment.

Not applicable

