### 7.4 Test Article(s) (Study Drug(s) and/or Study Device(s))

#### 7.4.1 Description

Provide a brief description of all test articles (drugs (including any foods and dietary supplements), devices and/or biologics used in the research including the purpose of their use and their approval status with the Food and Drug Administration (FDA). Include information about the form of the drug product (e.g., tablets, capsules, liquid).

Contrast enhanced ultrasound utilizes standard ultrasound units with a contrast software package included on the machine. The test utilizes Lumason (Bracco), which comes in a sterile vial as a powder. It is reconstituted at the time of use with sterile saline (provided in the Lumason package). Each kit provides the equivalent of two liver doses (2.4 mL each). The reconstituted liquid Lumason is then injected intravenously, followed by a flush with sterile saline (5-10 mL saline after each Lumason dose). Lumason is FDA approved for liver lesion evaluation in adults, which is what this study is evaluating (specifically, liver lesions in patients with hepatocellular carcinoma after treatment). After TACE treatment, the liver lesion may shrink, but does not entirely disappear, so contrast ultrasound will be evaluating the residual lesion that is left – is there residual viable tumor left, or not.

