### 8.3 Statistical methods

Describe the statistical methods (or non-statistical methods of analysis) that will be employed.

Patient demographics and major clinical information described above will be summarized using descriptive statistics. The main outcome variables in primary objective are the incidence of residual tumor and new tumor, which are both binary. The rate of residual/new tumors using CEUS and CT/MRI will be compared using McNemar's test, which is suitable for comparing paired binary variables. The point estimate and 95% confidence interval (CI) of the incidence rate for CEUS and CT/MRI will be reported separately. Due to the limited sample size of this pilot study, the non-inferiority between CEUS vs CT/MRI will be evaluated just by comparing the CIs of the incidence rate for each method, not by a formal statistical non-inferiority test which requires a much larger sample size. A few additional subgroup analyses will be performed to see if the incidence rate varies by stratification (such as BMI group, liver disease type). Due to the exploratory nature of this study no multiple regression models will be used, and no adjustment of the alpha rate will be made due to multiple testing. Treating the CT/MRI as the clinical gold standard, the sensitivity and specificity of CEUS will be estimated with their 95% CIs. The data from secondary objective will be analyzed similarly as those for the primary objective. For tertiary objective, the subjective ratings from patients between the CT/MRI and ultrasound will be compared using nonparametric Wilcoxon Signed-rank tests. The ratings may be further correlated with some of the baseline demographic and clinical factors using nonparametric Kruskal-Wallis tests. All analyses will be performed using statistical software SAS version 9.4 or higher (SAS Institute, Cary, NC, USA). All tests are two-sided and the significance level to be used is 0.05.

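### Enrolled patients removed because the treated lesion is not visible on ultrasound are neither counted nor given a place in the analysis, so the accuracy and rate results apply only to visible lesions

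*Combined protocol and SAP*

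**What the plan says.** **The removal rule.** Under section 3.3.1 a patient enrolled at TACE "will be excluded if the treated lesion is not visible on the grayscale ultrasound at timepoint 1", and contrast is not given. The same section removes patients who do not come back for the scheduled CT/MRI.

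**What happens to their data.** In section 3.3.2 the template asks what is collected on withdrawn subjects and whether they are replaced. The answer is "Not applicable".

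**The analysis.** Section 8.1 gives 34 enrolled and no evaluable number. Section 8.3 plans McNemar's test on residual and new tumour, rates with CIs for each modality and, with CT/MRI as reference, that "the sensitivity and specificity of CEUS will be estimated with their 95% CIs". It names no analysis set and does not mention patients without a CEUS. The nearest texts are general: data entry (7.2), monthly monitoring of enrolment (7.4.4) and periodic review of overall enrolment (17.6). None commits to reporting these patients.

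**The aims.** Section 1.1 sets out to determine "if contrast enhanced ultrasound (CEUS) is non-inferior to CT or MRI in patients with hepatocellular carcinoma (HCC) following transcatheter arterial chemoembolization (TACE) treatments", with no restriction to visible lesions. Section 1.3 asks in which patients CEUS may fall short because of the limits of ultrasound. Section 8.2 gives feasibility and input to a formal power calculation as purposes of the pilot.

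**Related text.** Sections 7.1 and 7.4.3 say without exception that every patient gets the CEUS. Exclusion 5 (3.2) keeps out patients whose tumour could not be seen on a recent non-contrast ultrasound, a failure it describes as "most commonly due to severe steatosis or obesity".

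**The concern.** The removal happens after enrolment and depends on how the ultrasound examination itself performs. CT/MRI faces no matching filter. If the plan is followed as written, the report would give an accuracy figure for patients in whom ultrasound worked, with no denominator to show how often it did not.

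That matters for three of the protocol's own aims. A conclusion about post-TACE patients in general (1.1) would rest on a subset. The clearest cases of ultrasound being limited, which 1.3 wants identified, would leave the data. The share of patients in whom CEUS cannot be done, a main feasibility result under 8.2, would go unreported. The protocol has reason to expect such cases: 2.2 reports that steatosis and adiposity limited visualisation in the team's own series, and 2.1 justifies the trial by a more obese U.S. population.

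**Working it through.** There is no plan figure to reproduce: 8.2 states that no formal sample size calculation was done. The check is an illustration of how far the two sets of estimates can differ.

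**Inputs**
- From the protocol: 34 enrolled (8.1).
- Assumed, because the protocol gives no values: sensitivity s = 90% and specificity c = 90% in visible lesions; p = 50% of all enrolled CT/MRI-positive; non-visible share f = 5, 10, 20 or 30%.
- Assumed share q of non-visible patients who are CT/MRI-positive: 50% (visibility independent of tumour status), 25%, or 0.
- Coding throughout: non-diagnostic CEUS = tumour not detected.

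**Formulas**
- Sensitivity, all enrolled = s × (1 − f·q/p)
- Specificity, all enrolled = c × (1 − g) + g, with g = f(1 − q)/(1 − p)
- Prevalence among visible: v = (p − f·q)/(1 − f)
- CEUS minus CT/MRI rate, visible only: D_vis = (1 − c)(1 − v) − (1 − s)v = 0.1 − 0.2v
- CEUS minus CT/MRI rate, all enrolled: D_all = (1 − f)·D_vis − f·q

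Example, q = 50%, f = 20%: sensitivity = 0.90 × (1 − 0.20 × 0.5/0.5) = 72%; g = 0.20, so specificity = 0.90 × 0.80 + 0.20 = 92%; v = 0.5, D_vis = 0 and D_all = −0.20 × 0.5 = −10 points.

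| Quantity | q | f = 5% | 10% | 20% | 30% |
|---|---|---|---|---|---|
| Sensitivity, all enrolled (%) | 50% | 85.5 | 81 | 72 | 63 |
| | 25% | 87.8 | 85.5 | 81 | 76.5 |
| | 0 | 90 | 90 | 90 | 90 |
| Specificity, all enrolled (%) | 50% | 90.5 | 91 | 92 | 93 |
| | 25% | 90.8 | 91.5 | 93 | 94.5 |
| | 0 | 91 | 92 | 94 | 96 |
| Rate difference, all enrolled (points) | 50% | −2.5 | −5 | −10 | −15 |
| | 25% | −1.5 | −3 | −6 | −9 |
| | 0 | −0.5 | −1 | −2 | −3 |
| Rate difference, visible only (points) | 50% | 0 | 0 | 0 | 0 |
| | 25% | −0.3 | −0.6 | −1.3 | −2.1 |
| | 0 | −0.5 | −1.1 | −2.5 | −4.3 |

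Sensitivity falls whenever q is above 0. The rate difference need not move against CEUS: D_all − D_vis = −f(D_vis + q), which turns positive when q is smaller than −D_vis. With q = 0 the visible-only set is therefore slightly the less favourable to CEUS. Independence is the harshest of the three cases shown, but it is not a bound.

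**In counts, under independence.** Take 34 enrolled, 17 positive, 6 non-visible (3 positive), one visible miss and one visible false positive. Intervals are Clopper-Pearson.
- Sensitivity: 13/14 = 93% (66 to 100%) visible only; 13/17 = 76% (50 to 93%) all enrolled.
- Specificity: 13/14 = 93%; 16/17 = 94%.
- CEUS versus CT/MRI rate: 14/28 versus 14/28; 14/34 = 41% versus 17/34 = 50%.
- Discordant pairs: 1 versus 1 (exact McNemar p = 1.0); 4 versus 1 (p = 0.375).

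**What the pilot could report.** Non-visible 6/34 = 18% (95% CI 7 to 34%); 0/34 would still have an upper limit of 10%. With no replacement rule, 34 × (1 − f) leaves about 32, 31, 27 or 24 evaluable.

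**The case against.** The strongest reply is that the rule is stated openly and that accuracy among visible lesions is a legitimate quantity. Objectives are normally read together with eligibility and removal rules, and exclusion 5 applies the same idea before enrolment. This stands: nothing is hidden, and the conditional estimate may remain the main one. What it does not supply is the count, the label and the limit on the conclusion. Nor does exclusion 5 close the gap. It acts at consent and only for patients with an ultrasound in the preceding 3 months, whereas Timepoint 1 falls 2 to 4 months after TACE (1.2).

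It is also fair to say that little changes in the pilot's own inference. Section 8.3 disclaims a formal non-inferiority test, and in the worked counts the intervals overlap widely and McNemar's test is non-significant in both sets. Coding an examination that was never done as not detected mixes technical failure with misreading and credits specificity; it is one choice among several.

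A reader might infer more than the protocol supports:
- *That removal tracks tumour response.* Section 7.4.1 says "the liver lesion may shrink, but does not entirely disappear", and exclusion 5 points mainly to steatosis or obesity. A link to response is possible but not shown. Through shrinkage it would tend to make removed patients less often positive, which reduces the loss of sensitivity.
- *That the planned BMI subgroup analysis would conceal a difference in sensitivity.* Section 8.3 plans incidence rates, not sensitivity, by BMI group.
- *That a later power calculation would necessarily be optimistic.* That holds for sensitivity only if the later trial targets all post-TACE patients and some removed patients are CT/MRI-positive. If it keeps the same visibility rule, the conditional estimate is the right planning input.

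**Conclusion.** The point holds as a gap in counting, analysis-set definition and labelling, and should be fixed. Sections 3.3.1, 3.3.2 and 8.3 together make the planned accuracy and rate estimates conditional on a visible treated lesion, while 1.1, 1.3 and 8.2 ask broader questions. That part rests on the text alone and needs no assumption.

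The size is unknown. The figures above depend on an assumed non-visible share, assumed 90% accuracy in visible lesions, an assumed 50% prevalence and one coding. The sign for sensitivity is settled under that coding: lower if any removed patient is CT/MRI-positive, unchanged if none is. The sign for the rate difference is not settled. To conclude that the trial's results are biased in favour of CEUS by a known amount, or on every measure, would go beyond the protocol.

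**What to change.** Who receives contrast does not change.

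- **3.3.1 and 3.3.2:** keep these patients in the data set as CEUS non-diagnostic, with baseline data and the routine Timepoint 1 and Timepoint 2 CT/MRI results retained where available.
- **8.3, reporting:** give the non-visualisation proportion with its 95% CI, overall and by BMI group.
- **8.3, labelling:** describe the planned accuracy and rate estimates, and any non-inferiority statement drawn from them, as conditional on a visible treated lesion.
- **8.3, supportive analysis:** analyse all enrolled patients who have a Timepoint 1 CT/MRI, with one pre-stated coding of non-diagnostic CEUS used for sensitivity, specificity and McNemar's test alike. If the coding is not detected, note that it favours specificity.
- **7.1 and 7.4.3:** reconcile the statements that every subject receives the CEUS with 3.3.1.

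The cost is a text amendment and a few sentences in 8.3. CT/MRI is already standard of care, so no procedure is added. The downside is a second, possibly less favourable set of figures, and wide intervals for the non-visualisation proportion, especially within BMI groups.

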#### 3.3.2 Follow-up for withdrawn subjects

Describe when and how to withdraw subjects from the study; the type and timing of the data to be collected for withdrawal of subjects; whether and how subjects are to be replaced; the follow-up for subjects withdrawn from investigational treatment.

Not applicable

## 4.0 Recruitment Methods

- Upload recruitment materials for your study in CATS IRB (<http://irb.psu.edu>). **DO NOT** include the actual recruitment wording in this protocol.
- StudyFinder: If StudyFinder (<http://studyfinder.psu.edu>) is to be used for recruitment purposes, separate recruitment documents do not need to be uploaded in CATS IRB. The necessary information will be captured from the StudyFinder page in your CATS IRB study.
- Any eligibility screening questions (verbal/phone scripts, email, etc.) used when contacting potential participants must be uploaded to your study in CATS IRB (<http://irb.psu.edu>).

### 4.1 Identification of subjects

Describe the source of subjects and the methods that will be used to identify potential subjects (e.g., organizational listservs, established recruitment databases, subject pools, medical or school records, interactions during a clinic visit, etc.). If not recruiting subjects directly (e.g., database query for eligible records or samples) state what will be queried, how and by whom.

StudyFinder:

- If you intend to use StudyFinder (<http://studyfinder.psu.edu>) for recruitment purposes, include this method in this section.
- Information provided in this protocol needs to be consistent with information provided on the StudyFinder page in your CATS IRB study.

For Penn State Health submissions using Enterprise Information Management (EIM) for recruitment, and for non-Hershey locations as applicable, attach your EIM Design Specification form on in CATS IRB (<http://irb.psu.edu>). See “HRP-103- Investigator Manual, What is appropriate for study recruitment?” for additional information. **DO NOT** include the actual recruitment material or wording in this protocol.

All patients at Penn State Hershey Medical Center who have a TACE ordered by a referring clinician will be identified as potential subjects. Opportunities for enrollment occur at the clinician office if one of the sub-PIs is treating the patient, and also within the Cardiovascular Interventional Radiology (CVIR) suite, where all patients are treated for TACE. All applicable patients will be approached at one of those times for enrollment.

### 4.2 Recruitment process

Describe how potential subjects first learn about this research opportunity or indicate as not applicable if subjects will not be prospectively recruited to participant in the research. Subject recruitment can involve various methods (e.g., approaching potential subjects in person, contacting potential subjects via email, letters, telephone, ResearchMatch, or advertising to a general public via flyers, websites, StudyFinder, newspaper, television, and radio etc.). **DO NOT** include the actual recruitment material or wording in this protocol.

#### 4.2.1 How potential subjects will be recruited.

Potential subjects will be recruited during a clinic visit, if seen by a sub-PI, or at the time of their TACE treatment in the CVIR. A screening checklist will be used by the consenting physician to ensure eligibility. Information on the screening checklist will be gleaned from the patient's medical record and/or information collected from the TACE consent.

#### 4.2.2 Where potential subjects will be recruited.

Recruitment may occur in the clinicians' office visit if conducted by one of the sub-investigators, or within the CVIR suite, at the time of their TACE treatment. Subjects will be enrolled in either the clinical visit room or in the dedicated Image-guided Procedure Unit in the Department of Radiology.

**4.2.3 When potential subjects will be recruited.**

Subjects will be recruited during their clinicians' office visit, if conducted by one of the sub-investigators, or at the time of consent for their standard-of-care TACE procedure.

**4.2.4 Describe the eligibility screening process and indicate whether the screening process will occur before or after obtaining informed consent. Screening begins when the investigator obtains information about or from a prospective participant in order to determine their eligibility. In some studies, these procedures may not take place unless HIPAA Authorization is obtained OR a waiver of HIPAA Authorization when applicable for the screening procedures is approved by the IRB. [For FDA regulated studies, consent for any screening activities would need to be obtained prior to screening unless specifically waived by the IRB.]**

The eligibility screening process will occur after obtaining informed consent for the research. Information on the screening checklist will be gleaned from the patient's medical record and/or information collected from the TACE consent.

## 5.0 Consent Process and Documentation

Refer to the following materials:

- The "HRP-090- SOP - Informed Consent Process for Research" outlines the process for obtaining informed consent.
- The "HRP-091- SOP - Written Documentation of Consent" describes how the consent process will be documented.
- The "HRP-314- Worksheet - Criteria for Approval" section 7 lists the required elements of consent.
- The "HRP-312- Worksheet - Exemption Determination" includes information on requirements for the consent process for exempt research. In addition, the CATS IRB Library contains consent guidance and templates for exempt research.
- The CATS IRB library contains various consent templates for expedited or full review research that are designed to include the required information.
- Add the consent document(s) to your study in CATS IRB (<http://irb.psu.edu>). Links to Penn State's consent templates are available in the same location where they are uploaded. **DO NOT** include the actual consent wording in this protocol.

